This SAP describes the datasets and the statistical methods to be used for the reporting and analysis of all data collected during the trial, except:

- Qualitative interview data (description of the BPL-003 subjective experience), psychological change measures and semi-structured interviews which will be analysed and reported separately
- Treatment model, feedback from therapists which will be reported separately

If a future protocol amendment necessitates a substantial change to the statistical analysis of the trial data, this SAP will be amended accordingly. If, after database lock, additional analyses are required to supplement the planned analyses described in this SAP, those unplanned analyses will not be described in an amended SAP, but they will be identified in the integrated clinical study report (CSR). Any deviations from this SAP will be documented in the CSR.

This SAP has been written in consideration of the following guidelines:

- International Conference on Harmonization (ICH) E9, Guidance for Industry: Statistical Principles for Clinical Trials (ICH E9 1998¹); and
- ICH E3, Guidance for Industry: Structure and Content of Clinical Study Reports (ICH E3 1995)².

Statistical analysis will be done using SAS[®] 9.4 or higher on a Windows PC.

4 Study objective(s) and endpoint(s)

4.1 Study objective(s)

4.1.1 Primary objective

- To assess the safety and tolerability of single intranasal dose of BPL-003 (5-methoxy-N,N-dimethyltryptamine (5-MeO-DMT)) in patients with alcohol use disorder (AUD)

4.1.2 Secondary objective(s)

- To assess the pharmacodynamics (PD; including psychological effects) of single intranasal doses of BPL-003 in patients with AUD
- To assess the feasibility of the treatment model for BPL-003 combined with relapse prevention psychotherapy in patients with AUD

4.1.3 Exploratory objective(s)

- To explore the effects of a single intranasal dose of BPL-003 combined with relapse prevention psychotherapy in patients with AUD on alcohol use and related symptoms
- To explore the effects of BPL-003 combined with relapse prevention psychotherapy on health-related quality of life (QOL) in patients with AUD
- To explore exposure levels after a single intranasal dose of BPL-003 in patients with AUD
- To assess the correlation of PD effects with alcohol use and related symptoms
- To determine participant expectations of treatment outcome

4.2 Study endpoint(s)

4.2.1 Primary endpoint(s)

Safety Endpoints:

- Percentage of patients with treatment-emergent adverse events (TEAEs)
- Percentage of patients with clinically significant postdose abnormal laboratory tests
- Percentage of patients with clinically significant abnormal postdose vital sign measurements (Heart rate (HR), Blood Pressure (BP), and body temperature)
- Percentage of patients with postdose suicidal ideation as determined by the Columbia-Suicide Severity Rating Scale (C-SSRS)
- Change in C-SSRS score compared to Baseline at Days 7 and 84
- Readiness for discharge questionnaire
- Measure the frequency, emotional valence and functional impact of any re-activation events in the study through the Reactivation Questionnaire (ReAQ)

4.2.2 Secondary endpoint(s)

Pharmacodynamic Endpoints:

- The effects of BPL-003 as determined by the Mystical Experience Questionnaire (MEQ-30) and Ego Dissolution Inventory (EDI)
- Percentage (%) of patients experiencing a complete mystical experience, as assessed by the MEQ-30 on Day 0
- Description of the BPL-003 subjective experience data (from the qualitative interview)#
- Psychological change as measured with a questionnaire and semi-structured interview

Treatment Model:#

- Treatment model, feedback from therapists on
 - Frequency and duration of psychotherapy sessions
 - Implementation of therapy manuals
- Overall therapy model

4.2.3 Exploratory endpoint(s)

Pharmacokinetic:

- Blood samples to determine 5-MeO-DMT and its metabolites (including bufotenine) plasma concentrations will be taken after dosing on Day 0.

Drinking Cravings and withdrawal:

- Change in alcohol craving as measured by Alcohol Craving Questionnaire (ACQ) at Days 1, 7, 28, 56, and 84 compared to Baseline (pre-dose Day 0)
- Alcohol cravings as measured by Craving Visual Analogue Scale (VAS)
- Alcohol withdrawal symptoms as measured by Clinical Institute Withdrawal Assessment (CIWA-Ar)

Alcohol Use:

- Using the Timeline Follow-Back (TLFB) interview, the following parameters of alcohol use in the 90 days before dosing and endpoint will be recorded:
 - Longest duration (days) of continuous abstinence
 - Maximum number of standard units of alcohol consumed on any one day
 - Number of Heavy Drinking Days (HDD)
 - Percentage of Heavy Drinking Days (PHDD) in 85d prior D-3 (or start of detox) vs PHDD post-dosing measured on d14, d28, d56, d84
 - Percentage of drinking days (PDD) in 85d prior D-3 (or start of detox) vs PDD post-dosing measured on d14, d28, d56, d84.
 - Mean Units per day (UPD): In 85d prior D-3 (or start of detox) vs UPD post-dosing measured on d14, d28, d56, d84.
 - Abstinence: Percentage of Abstinent days (PAD) in 85d prior D-3 (or start of detox) vs PAD on d14, d28, d56, d84 (with biomarker verification).
 - Number of days after BPL-003 dosing to first drink
 - Number of days after BPL-003 dosing to first HDD (defined by UK government as ≥ 7 units a day for a woman and ≥ 9 units per day for a man)
 - Average number of standard units of alcohol consumed per week in 85d prior D-3 (or start of detox) vs post-dosing measured on d14, d28, d56, d84 (and reported referencing UK risk levels)
- Consequences of alcohol use as measured by Short Inventory of Problems (SIP)
- Biomarkers:
 - Alcohol use as measured by Ethylglucuronide (EtG) in urine at Days 1, 28, 56, 84 compared to Screening
 - Alcohol use as measured by carbohydrate deficient transferrin (CDT) in blood at Days 28 & 84 compared to Screening

Pharmacodynamic

- The correlation of the occurrence of a “complete mystical experience” and “ego dissolution”, measured by the MEQ-30 and EDI, with improvement in alcohol use and craving (measured by ACQ, TLFB, EtG, CDT)

Wellbeing:

- Change in Montgomery–Asberg Depression Rating Scale (MADRS) at Days 28, 56, and 84 compared to Baseline
- Change in Clinical Global Impression Severity (CGIS) at Days 1, 28, 56, and 84 compared to Baseline
- Patient Global Impression of Change (PGIC) at Days 1, 28, 56, and 84
- Change in 5-level EuroQol-5 Dimension (EQ-5D-5L) at Days 28 and 84 compared to Baseline

Expectation:

- Assess positive and negative expectations as measured by Stanford Expectations of Treatment Scale (SETS)

denotes to be reported separately

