Historically, psychoactive substances were used, among other reasons, to facilitate mystical/peak experiences in ceremonial settings in different cultures (Schultes, 2001). These experiences are characterised by a sense of unity, sacredness, ineffability, transcendence of time and space, and deeply felt positive mood (Johnson, 2019). Drug-occasioned mystical experiences are hypothesised to be a mediating mechanism underlying the therapeutic effects of psychedelics, and there is robust research evidence that the occurrence of a mystical experience while under the effects of a psychedelic is one of the most reliable predictors of treatment outcomes (Griffiths, 2016; Johnson, 2019; Richards, 1977; Ross, 2016), most notably improvements in SUDs (Bogenschutz, 2015; Garcia-Romeu, 2014; Johnson, 2014; Krebs, 2012; Savage, 1973). In a smoking cessation study (Johnson, 2017), the strength of mystical experiences during psilocybin sessions correlated with clinical change in addictive behaviour. Similarly, in a study of psilocybin for alcohol dependence (Bogenschutz, 2015), ratings of mystical experiences correlated strongly with reductions in drinking behaviour. Links between the strength of mystical experience and therapeutic outcomes in treatment-resistant depression (TRD) were noted in a small open-label study by Carhart-Harris et al (Carhart-Harris, 2017a; Carhart-Harris, 2016; Carhart-Harris, 2018), but also in larger, controlled studies of anxiety and depression associated with life-threatening illness (Grob, 2011; Ross, 2016). The occurrence of mystical experience during a psychedelic session predicted positive outcomes for individuals more than a year later (Griffiths, 2008; Schmid, 2018), and its importance for long-term outcomes occurs regardless of the genesis of the experience (Griffiths, 2011; Russ, 2019).

1.3. 5-Methoxy-N,N-dimethyltryptamine

5-Methoxy-N,N-dimethyltryptamine (5-MeO-DMT) is a tryptamine that falls into the category of “classic” psychedelics (Nichols, 2004; 2016). It is endogenously produced in humans, although its biological function, if any, is not known (Barker, 2012; Guchhait, 1976; Narasimhachari, 1971).

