3.3. Exploratory Endpoints

Pharmacokinetic:

- Blood samples to determine 5-MeO-DMT and its metabolites (including bufotenine) plasma concentrations will be taken after dosing on Day 0.

Drinking Craving:

- Change in alcohol craving as measured by Alcohol Craving Questionnaire (ACQ) at Days 1, 7, 28, 56, and 84 compared to Baseline (pre-dose on Day 0)
- Alcohol cravings as measured by Craving Visual Analogue Scale (VAS)
- Alcohol withdrawal symptoms as measured by Clinical Institute Withdrawal Assessment (CIWA-Ar)
- Consequences of alcohol use as measured by Short Inventory of Problems (SIP)

Alcohol Use:

Using the Timeline Follow-Back (TLFB) interview, the following parameters of alcohol use in the 90 days before dosing and endpoint will be recorded:

- Percentage of Heavy Drinking Days (PHDD) in 85d prior D-3 (or start of detox) vs PHDD post-dosing measured on d14, d28, d56, d84.
- Percentage of drinking days (PDD) in 85d prior D-3 (or start of detox) vs PDD post-dosing measured on d14, d28, d56, d84.
- Mean Units per day (UPD): In 85d prior D-3 (or start of detox) vs UPD post-dosing measured on d14, d28, d56, d84.
- Abstinence: Percentage of Abstinent days (PAD) in 85d prior D-3 (or start of detox) vs PAD on d14, d28, d56, d84 (with biomarker verification).
- Longest duration (days) of continuous abstinence
- Number of days after BPL-003 dosing to first drink
- Number of days after BPL-003 dosing to first HDD (defined by UK government as >7 units a day for a woman and >9 units per day for a man)
- Average number of standard units of alcohol consumed per week in 85d prior D-3 (or start of detox) vs post-dosing measured on d14, d28, d56, d84 (and reported referencing UK risk levels)
- Maximum number of standard units of alcohol consumed on any one day

Correlation of PD effects with alcohol use and related symptoms

The correlation of the occurrence of a “complete mystical experience” and “ego dissolution”, measured by the MEQ30 and EDI, with improvement in alcohol use and craving (measured by AQC, TLFB, EtG, CDT)

Biomarkers

- Alcohol use as measured by EtG in urine at Days 1, 28, 56, 84 compared to Screening
- Alcohol use as measured by CDT in blood at Days 28 & 84 compared to Screening

Wellbeing

- Change in Montgomery–Asberg Depression Rating Scale (MADRS) at Days 28, 56, and 84 compared to Baseline
- Change in Clinical Global Impression Severity (CGIS) at Days 1, 28, 56, and 84 compared to Baseline

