15.1 Pharmacokinetic concentration data

Plasma concentrations of 5-MeO-DMT and its metabolites (bufotenine, 5-methoxyindolacetic acid (5-MIAA) and 5-MeO-DMT-N-Oxide) will be listed and summarised by treatment.

Using actual sample times, linear and semi-logarithmic concentration-time plots of each patient will be prepared. The same linear and logarithmic scales will be used for each patient. The linear and semi logarithmic plots for a given patient will be presented on the same page. For clarity in presentation, individual profiles for different analytes will be separate.

Nominal blood sampling times will be used to calculate the mean (SD) drug concentrations at each time point. Comparative linear and semi logarithmic plots of the mean (\pm SD) concentration-time data for each group will be prepared.

For individual concentration–time plots, plasma concentrations below the limit of quantification of the assay (BLQ) will be treated as follows: values that occur before t_{max} will be taken as zero; all other values will be taken as missing.

For calculation of plasma concentration summary statistics, BLQ values will be taken as zero, unless they fall between two quantifiable concentrations, in which case they will be treated as missing.

16 Pharmacodynamic analyses

PD data will be summarised using the ITT and PP (alcohol use from the TLFB interview, and MEQ only) Population.

PD data will be listed by treatment and time point and summarised by treatment and time point. Changes from baseline questionnaires will be summarised by time point and treatment.

The PD data includes the following psychometric scales and questionnaires: Stanford Expectation of Treatment Scale (SETS), Mystical Experience Questionnaire (MEQ-30), Ego Dissolution Inventory (EDI), 5-Level EuroQol 5-Dimension (EQ-5D-5L), Timeline Follow-Back (TLFB), Montgomery-Åsberg Depression Rating Scale (MADRS), Alcohol Craving Questionnaire (ACQ), Craving Visual Analogue Scale (VAS), Clinical Global Impression of Severity (CGI-S), Patient Global Impression of Change (PGIC), Clinical Institute Withdrawal Assessment for Alcohol-Revised (CIWA-Ar), Short Inventory of Problems (SIP).

Each psychometric scale/questionnaire will be reported using standard scales as described in Appendix A: Pharmacodynamic analysis.

The scales will be listed and summarised.

In addition, an individual plot of the mean units of alcohol per day (UPD) from the TLFB questionnaire will be produced.

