									n	Mean	SD	Median	Min	Max
Apparent Sadness	Treatment 1 (N=xx)													
↓														
Total MADRS Score	Treatment 1 (N=xx)													

Source: Listing 16.2.xx

Programming notes: For MADRS, include all individual questions treated as continuous data
Continued for all scores (subscales and/or total score) & time points for all questionnaires described in Appendix A. Update column 1 to match the data
For Alcohol Craving questionnaire, the first column will be "Scoring Item"

Template T_PD2a

Table 14.3.4.xx Summary of patients with 50% reduction from baseline of MADRS scores

Treatment	Responder at Day 28 n (%)	Responder at Day 56 n (%)	Responder at Day 84 n (%)
Treatment 1 (N=xx)			

Source: Listing 16.2.xx

Note: Percentages are based on the number of non-missing observations

Programming notes: Continued with all time points

Template T_PD2b

Table 14.3.4.xx Summary of patients in remission based on MADRS scores ≤ 10

Treatment	Planned Relative Time	Total MADRS score ≤ 10 n (%)
Treatment 1 (N=xx)	Time 1	

Source: Listing 16.2.xx

Note: Percentages are based on the number of non-missing observations

Programming notes: Continued with time points.

Template T_PD3

Table 14.2.2.xx Summary of complete mystical experience

Treatment 1 (N=xx)	
Planned Relative Time	n (%)
Time 1	

Source: Listing 16.2.xx

A complete mystical experience is defined as a patient scoring 3 or more on each of the four subdomains

Programming notes: Continued for all timepoints

Template T_PD4

Table 14.2.2.xx Summary of 5-Level EuroQoL 5-Dimension (EQ-5D-5L)

Item Assessed	Question	Planned Relative Time	Treatment 1 (N=xx)
Mobility (%)	I have no problems in walking about	Time 1	
		Time 2	
	I have slight problems in walking about	Time 1	
		Time 2	
	I have moderate problems in walking about	Time 1	
Self-care (%)	↓		
	I have no problems washing or dressing myself	Time 1	
	↓	Time 2	
Usual activities (%)	I have no problems doing my usual activities	Time 1	
	↓		
Pain/Discomfort (%)	I have no pain or discomfort	Time 1	
	↓		
Anxiety/Depression (%)	I am not anxious or depressed	Time 1	
	↓		
How good or bad your health is today (mm)	n	Time 1	
	Mean		
	SD		
	Median		
	Min		
	Max		

Programming notes: Continued with all Items assessed, questions, treatment groups and time points.

Template T_PD5

Table 14.2.2.xx Summary of Montgomery-Asberg Depression Rating Scale (MADRS)

Question	Treatment	Planned								Change from Baseline					

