19.3 Table of footnotes for data display specifications (questionnaires only)

Listing/Table Number	Description	Footnotes
16.2.6.2	Listing of Stanford Expectation of Treatment Scale	SETS is a 10 item scale with 6 items used to calculate expectancy
16.2.6.3	Listing of Mystical Experience Questionnaire (MEQ-30)	Total MEQ-30 Score = (Mystical Subdomain + Positive Mood Subdomain+ Transcendence Subdomain + Ineffability Subdomain) / 4 A 'complete mystical experience' is defined as a patient scoring 3 or more on each of the four subdomains.
16.2.6.4	Ego-Dissolution Inventory (EDI)	The EDI is an 8-item measure which will be used to measure the acute ego dissolution experience during dosing using visual analogue scale (VAS) from 0 ('No, not more than usually') to 100 ('Yes, entirely or completely'). Total score is calculated as mean of all 8 items.
16.2.6.12	Clinical Institute Withdrawal Assessment for Alcohol-Revised (CIWA-Ar)	The maximum score is 67; mild alcohol withdrawal is defined by a score ≤ 10 , moderate by scores 11 to 15, and severe by any score ≥ 16 .

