2.2 Analysis and reporting

Factor scores are computed by calculating the mean response to the following items:

- Mystical items are: 4, 5, 6, 9, 14, 15, 16, 18, 20, 21, 23, 24, 25, 26, 28.
- Positive mood items are: 2, 8, 12, 17, 27, 30.
- Transcendence items are: 1, 7, 11, 13, 19, 22.
- Ineffability items are: 3, 10, 29.

The MEQ30-total score is computed by taking the mean response to all items.

3 Ego Dissolution Inventory (EDI)

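### The SAP lists a correlation of the psychedelic experience with drinking and craving but plans no analysis of it, and the wording points to a yes/no predictor although scores are already derived

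*SAP*

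**What the plan says.** The objective in SAP 4.1.3 reads "To assess the correlation of PD effects with alcohol use and related symptoms". The matching endpoint in SAP 4.2.3 is "The correlation of the occurrence of a “complete mystical experience” and “ego dissolution”, measured by the MEQ-30 and EDI", and Protocol 3.3 completes it "with improvement in alcohol use and craving (measured by AQC, TLFB, EtG, CDT" (AQC evidently means the ACQ). For the MEQ-30 the cut is stated in the shell for the complete-experience table: "A complete mystical experience is defined as a patient scoring 3 or more on each of the four subdomains". The footnote table in SAP 19.3 repeats it. Neither document gives an EDI value above which ego dissolution counts as having occurred.

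Continuous versions exist. Appendix A 2.2 derives four subdomain means and a total: "The MEQ30-total score is computed by taking the mean response to all items". Appendix A 3.2 derives the EDI as the mean of its 8 items.

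Protocol 11.7.1 leaves further PD analysis to the SAP. SAP section 16 says "The scales will be listed and summarised" and adds one individual plot of units per day. The items to be reported separately are the interviews, the psychological change measures and the therapist feedback, and this endpoint is not among them. Section 17 declares one change only, on laboratory flags.

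**The concern.** Two things look wrong. First, a listed objective has no route to a result. The measure of improvement, the day and the coefficient are all undefined, so any correlation in the study report would be chosen after the data are known. Under the SAP's own scope statement, an analysis added after database lock is an unplanned one.

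Second, if someone programs the endpoint from its wording, the natural MEQ-30 variable is a yes/no split of a graded score. That discards information in a study of at most 12 patients, and the EDI half cannot be programmed as an occurrence at all.

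At stake is the trial's one quantitative look at a premise it sets out at length in Protocol 1.2, that a stronger experience goes with more benefit.

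**Working it through.** **1. Is a correlation planned anywhere in the SAP?**
- Sections 4.1.3 and 4.2.3: named as objective and endpoint.
- Section 16: listings, summaries and a units-per-day plot.
- Section 19.1: MEQ-30 tables 14.2.3.1 to 14.2.3.4, EDI table 14.2.4, TLFB tables 14.2.6.1 and 14.2.6.2, ACQ table 14.2.8. None crosses the experience with an outcome. The PD figures are 14.2.5.1 and 14.2.5.2, both units per day.
- Section 19.2 shells and Appendix A: no coefficient, scatter plot, cross-tabulation or summary by experience status.
- Section 17: no removal declared.

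**2. How much choice is left open?** Counting the outcome scores and days that the SAP provides for the four named measures:
- ACQ: 5 scores x 5 days = 25
- TLFB: 5 measures shown with change from baseline (PHDD, PDD, units per day, PAD, units per week) x 4 days = 20
- EtG: 4 days
- CDT: 2 days

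The total is 25 + 20 + 4 + 2 = 51 outcome-by-day pairs per predictor. Some are redundant, such as drinking days and abstinent days.

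**3. What does a yes/no predictor cost?** The documents give no correlation or power figure to reproduce. Inputs: n = 12 (the planned maximum); rate p = 0.60, from 3 of 5 healthy volunteers at 10 mg and 12 mg (Protocol 1.4.2.3.1; 3/5 = 60%). Assumed: bivariate normal scores and a true correlation of 0.6.
- Attenuation = phi(z_p) / sqrt(p(1-p)) = 0.3863 / sqrt(0.24) = 0.3863 / 0.4899 = 0.789.
- Efficiency = 0.789^2 = 0.62, and 12 x 0.62 = about 7.5 patients' worth of information.
- Expected yes/no correlation = 0.6 x 0.789 = 0.473.
- 95% interval by Fisher z, half-width 1.96 / sqrt(12 - 3) = 0.653. Score: atanh(0.6) = 0.693, giving 0.04 to 0.87. Yes/no: atanh(0.473) = 0.514, giving -0.14 to 0.82.
- The rate in AUD is unknown (Protocol 4.3). By symmetry a 40% rate gives the same 0.79. At 80% the factor is 0.70 and the efficiency 0.49, or about 6 patients.
- Chance that all 12 fall on one side, leaving no correlation to compute: 0.6^12 + 0.4^12 = 0.2%; at 80%, 0.8^12 + 0.2^12 = 6.9%.

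The score figures above are for a Pearson correlation. Spearman gives part of the gain back. In simulation at a true correlation of 0.6, with n = 12 and a nominal two-sided 5% level, zero was excluded in 36% of trials with yes/no, 50% with Spearman and 58% with Pearson. These percentages only compare efficiency, because the trial plans no test.

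**4. Which MEQ-30 total?** The footnote in SAP 19.3 averages the four subdomains, so each weighs 25%. Appendix A 2.2 averages 30 items. The subdomains have 15, 6, 6 and 3 items, so they weigh 50%, 20%, 20% and 10%. The two totals differ unless the subdomain scores happen to balance, so a correlation needs one of them named.

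**The case against.** The best defence is that the SAP never sets out a yes/no analysis, so the loss in step 3 belongs to a method nobody has specified. The endpoint mentions measurement by the MEQ-30 and EDI, and the objective speaks of PD effects, so scores could be meant. That is fair. A reader might infer that the plan commits to dichotomising both scales. The documents do not support this: the yes/no reading is firm only for the MEQ-30, and for the EDI it would be an inference. The ambiguity is itself a reason to specify.

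A reader might also infer that the cut contradicts the protocol's rationale or lacks a source. Neither holds. Protocol 1.2 cites both the occurrence of a mystical experience and its strength or ratings as predictors, and Protocol 1.4.2.3.1 cites a published source for the cut. What does stand is narrower: the evidence that section 1.2 reports from alcohol dependence is that "ratings of mystical experiences correlated strongly with reductions in drinking behaviour".

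The study tests no hypotheses, so calling it underpowered would miss the point; the interval is the relevant measure. The real cut applies to the lowest of four bounded subdomain means, not to one normal score, so 0.79 is indicative. Nor do the documents suggest that the correlation is likely to be undefined: at the 60% rate the chance is 0.2%, and Protocol 4.3 raises a lower response in AUD, not a higher one.

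Finally, the endpoint is exploratory and patient-level listings are planned, so a correlation could be computed later. It would not be pre-specified.

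**Conclusion.** The concern holds, with the missing analysis as its main part. That part rests on reading the SAP and needs no assumption: the objective and endpoint are listed, not assigned to a separate report, not declared dropped, and have no method or output. It would go too far to conclude that the sponsor has abandoned the endpoint. The version 7.0 change log adds the correlation to the objectives as something previously missed in error.

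The yes/no wording is a secondary weakness. Its size (a factor of about 0.79, an efficiency of about 62%) depends on 12 patients, a bivariate normal model and a rate borrowed from 5 healthy volunteers per dose. Using the scores is better at almost no cost, but it will not make the estimate precise: at a true correlation of 0.6 even the score leaves an interval from about 0.04 to 0.87.

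**What to change.** Before database lock, in SAP 4.2.3, section 16 and Appendix A:
- Specify Spearman correlations with 95% confidence intervals, and scatter plots, for the MEQ-30 total and the EDI mean.
- Set them against change in a short named list, for example PHDD, units per day, ACQ general craving index and CDT, at one named day, for example Day 84. With two predictors that is 2 x 4 = 8 coefficients. Name the reference value for each (the 85-day window, predose Day 0 or Screening, as SAP 4.2.3 already has them).
- State which MEQ-30 total is used, and make SAP 19.3 and Appendix A 2.2 agree.
- State how EtG is handled, since the endpoint names it.
- Keep the complete-experience yes/no split as a descriptive display.
- Add the table and figure to 19.1, with shells, and align the wording of Protocol 3.3.

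If the analysis is not wanted, declare it dropped in section 17.

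The cost is SAP text, one table and one figure from data already collected. The small downside is that the yes/no label is no longer the headline predictor.
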